NCT05425719

CLINICAL STUDY PROTOCOL

A Pivotal, Open Label, Multi-Center, Safety and Pharmacokinetic Study of MB-102 (Relmapirazin) and the Use of the MediBeacon[®] Transdermal GFR Measurement System in Normal and Renal Compromised Subjects for the Evaluation of Kidney Function

| Protocol Number: | 100-003 |
|--------------------------|--|
| Investigational Product: | MB-102 (Relmapirazin) / MediBeacon [®] Transdermal GFR Measurement System |
| Phase: | Pivotal |
| Sponsor: | MediBeacon Inc. [name] USA |
| Date of Protocol | 20 September 2022 |
| Version of Protocol: | Version 4.0 |

CONFIDENTIAL

This protocol may not be reproduced or communicated to a third party without the written permission of MediBeacon Inc.

Statement of Compliance

The study will be conducted in compliance with the protocol, International Conference on Harmonization Good Clinical Practice E6 R2 (ICH-GCP), and the applicable regulatory requirements including the National Medical Products Administration Good Clinical Practice (NMPA GCP), The Code of Federal Regulations Title 21 CFR Parts 812, 11, 50, 54 and 56 and ISO 14155: 2020 (3rd Edition) Clinical Investigation of Medical Devices for Human Subjects – Good Clinical Practice

1 Synopsis

| Protocol Number: | 100-003 | | | | |
|---|--|--|--|--|--|
| Title: | A Pivotal, Open Label, Multi-Center, Safety and Pharmacokinetic Study of MB- 102 (Relmapirazin) and the Use of the MediBeacon [®] Transdermal GFR Measurement System in Normal and Renal Compromised Subjects for the Evaluation of Kidney Function | | | | |
| Investigational | MB-102 (Relmapirazin) | | | | |
| Products: | MediBeacon® Transdermal GFR Measurement System (TGFR) | | | | |
| Number of Study Sites: | This study will take place at up to 10 investigational sites in the US and China | | | | |
| Phase: | Pivotal | | | | |
| Objectives: To establish that the MB-102 transdermal fluorescence measured using the MediBeacon[®] Transdermal GFR Measurement System comparable to the measured MB-102 plasma GFR To evaluate the safety and tolerability of a single dose of MB-10 subjects To evaluate the safety and effectiveness of the MediBeacon[®] Tr GFR Measurement System for the non-invasive transdermal fluor detection of MB-102 in subjects | | | | | |
| Study Design: | Multi-center, pivotal open-label pharmacokinetic study comparing transdermal measured GFR (tGFR) to plasma-derived indexed GFR (nGFR). | | | | |
| Number of Treated Subjects: | Up to 250 subjects are planned for enrollment. The US sites will plan to enroll at least 140 evaluable subjects; Chinese sites will plan to enroll at least 48 evaluable subjects. The population will be split into stratums in accordance with screening eGFR measured by the CKD-EPI equation: | | | | |
| | • Stratum 1: 50% of evaluable subjects with an eGFR \ge 70 mL/min/1.73 m ² | | | | |
| | • Stratum 2: 50% of evaluable subjects with an eGFR < 70 mL/min/1.73 m^2 | | | | |
| | Approximately 50% of subjects within each Stratum enrolled in the US will be Fitzpatrick skin scale (FSS) I-III and 50% of subjects will have FSS IV-VI. Subjects in the US will be enrolled across a spectrum of both eGFR ($<120 - >15$ mL/min/1.73 m ²) and FSS. | | | | |
| | Subjects enrolled in China will also be represented across the same spectrum of eGFR (<120 - >15 mL/min/1.73 m ²) however the FSS will not apply. This is because the Chinese subject demographic is unlikely to represent the full FSS spectrum. Subjects with incomplete assessments or major protocol deviations may be replaced. Thus, a maximum of 250 subjects may be enrolled. | | | | |
| Treatment: | Eligible subjects in stratums 1 and 2 will receive a single 130 mg dose of MB-102. | | | | |
| | Blood draws will be taken at pre-defined timepoints and the MediBeacon [®] Transdermal GFR Measurement System fluorescent measurements will be collected over a 12 hour - 24 hour period. | | | | |

| Main Criteria for Inclusion: |
|--|
| Main Criteria for Inclusion: Age ≥ 18 years – male or female Eligible female non-pregnant subjects who are either not of child-bearing potential or willing to use adequate contraception during the trial Males must be willing to practice abstinence or utilize adequate contraception from dosing day to at least 7 days post-dose For women of child-bearing potential, the subject should have a negative serum pregnancy test at screening, and agrees to one of the following acceptable contraceptive methods used consistently and correctly i.e. abstinence, oral contraceptive either combined or progesterone alone; injectable progesterone, implants of levonorgestrel, estrogenic vaginal ring, percutaneous contraceptive patches, IUD device or system or male partner sterilization Men will not donate sperm during the study and for 1 month following the last dose of study drug Subjects who are capable of directly providing informed consent and who can comply with the requirements and restrictions required by the protocol Adequate venous access sufficient to allow blood sampling per protocol requirements Main Criteria for Exclusion: Subjects positive via PCR testing for COVID-19 Vaccinated subjects without symptoms of COVID-19 are not required to undergo PCR testing but may be tested at the discretion or loss of blood or plasma: 100 mL to 499 mL within 30 days prior to the initial dose of the study medication; or more than 499 mL within 56 days prior to the initial dose of study medication; or more than 499 mL within the following time ranges: prior to the first dosing day in the current study: either 30 days of Shalf-lives of the investigational product (whichever duration is longer). History of skin sensitivity to adhesives (e.g. Band-Aids, surgical tape) History of skin sensitivity to adhesives (e.g. Band-Aids, surgical tape) |
| |

| | study results in the judgement of the investigator and would make the subject inappropriate for entry into this study. 8. Significant scaring, tattoos or alterations in pigmentation on the sternum or other sensor location testing areas that would alter sensor readings versus other areas of the skin 9. Any serious or uncontrolled medical disorder, active infection, physical exam finding, laboratory finding, or psychiatric condition that in the opinion of the investigator would limit the subjects' ability to complete study requirements or may put the subject at increased risk or compromise the interpretability of study results. 10. Currently receiving dialysis 11. Currently anuric 12. Subjects with positive serum pregnancy test 13. Subjects with an eGFR > 120 mL/min/1.73m² | | | | | |
|------------------------------|---|--|--|--|--|--|
| Primary Endpoint: | The primary endpoint is the performance measure of P30 for transdermal- derived GFR with respect to the plasma-derived indexed GFR, with a 95% confidence interval. The performance goal is 85%. Success for the study will be that the lower limit of the 95% CI is greater than 85%. | | | | | |
| Safety Evaluation | Safety of MB-102 will be evaluated through treatment emergent adverse events (TEAEs), where treatment emergence is defined with respect to the first administration of MB-102. Safety of the MediBeacon[®] Transdermal GFR Measurement System will be evaluated through TEAEs, where treatment emergence is defined with respect to the start time of device use. | | | | | |
| Statistical Analyses | The primary endpoint is the performance measure of P30 for transdermal- derived GFR with respect to the plasma-derived indexed GFR, with a 95% confidence interval. The performance goal is 85%. Success for the study will be that the lower limit of the 95% CI is greater than 85%. Safety of MB-102 will be evaluated through treatment emergent adverse events (TEAEs), where treatment emergence is defined with respect to the administration of MB-102. | | | | | |
| | Safety of the MediBeacon [®] Transdermal GFR Measurement System will be evaluated through TEAEs, where treatment emergence is defined with respect to the start time of Transdermal GFR Measurement System use. Additional safety variables include physical examinations, vital sign measurements, ECGs, clinical laboratory assessments, and medication use. | | | | | |

3.1 Background

Therapeutic interventions for acute kidney injury (AKI) patients are delayed due to current clinical practice of reliance on a serum creatinine blood test (SCr) for an estimation of glomerular filtration rate (GFR). Typically, 24-72 hours elapse from onset of a kidney injury event to a SCr indicating a non-normal level (Stevens et al, 2006). Since AKI affects upwards of 20% of hospitalized patients and 70% of critically ill patients in the intensive care unit (ICU), this contributes to high mortality rates (approaching 60% for those requiring renal replacement therapy [Endre at al., 2011]), development of chronic kidney disease (affecting an estimated 27 million Americans, accounting for ~ 24% of Medicare costs [NIH 2008]), and consequent progression to end stage renal disease (with an estimated 400,000 Americans on dialysis [Kidney Disease Statistics for the US]).

Glomerular filtration rate (GFR) is widely accepted as the best indicator of kidney function and is a key component of the diagnosis and management of renal impairment. A simple, accurate, and point-of-care (POC) method for determining GFR is needed, as current methods for determining GFR are either: 1) practical but lack accuracy, or 2) accurate but prohibitively complex, especially for frequent and recurrent measurements.

Current medical practice for general renal function assessment relies on estimated GFR (eGFR). This involves estimation using equations based on a single serum creatinine (SCr) measurement, or a measurement of creatinine clearance (CrCl) based on a 24-hour collection of urine plus measurement of a single SCr concentration. Although readily available and convenient, measurement of SCr as an indicator of renal function is problematic because it is a lagging indicator of current renal function, lacks sensitivity, and may be misleading because it is affected by age, state of hydration, renal perfusion, muscle mass, dietary intake, and many other anthropometric and clinical variables (Agarwal, 2003 and Verhave et al., 2005). CrCl estimation using timed urine collections can be more accurate, but problems with completeness of 24-hour urine collection often result in under or over estimation of CrCl.

Measuring GFR using urinary or plasma clearance of exogenous filtration markers is the accepted standard for evaluation of kidney function. In the past three decades, renally filtered exogenous agents such as inulin, iohexol, ¹²⁵Iodine-iothalamate (¹²⁵I-iothalamate), and technetium-99m-diethylene triamine - pentaacetate (^{99m}Tc-DTPA) have all been used to determine GFR (Stevens et al., 2006). From both a safety and effectiveness standpoint, these agents are acceptable, although they contain iodine, which can cause anaphylactoid reactions, and they can be nephrotoxic when very high volumes are used. However, they are not used routinely to determine GFR because the protocols are time-consuming, complex, and expensive, which make their repeated use impractical in many clinical settings, and they may require imaging equipment and administration of radioactive agents (Stevens and Levey, 2009). Accurate measurement of GFR at the patient's bedside is highly desirable in order to assess the patient's renal function. There is a significant need to develop a simple, accurate, and POC method for measuring GFR (Erley et al., 2001).

To address this unmet clinical need, MediBeacon is developing a combination product that requires the administration of a fluorescent tracer agent designated relmapirazin (also known as MB-102 and formerly known as MP-3180) that will be detected transdermally by a sensor which is attached to a device monitor (called the MediBeacon[®] Transdermal GFR Measurement System [TGFR]).

MB-102 has been engineered to be excreted from the body by the renal system, and specifically by the GFR mechanism. Normal functioning kidneys will remove this agent from the body with an approximate 2 hour half-life. Impaired functioning kidneys will take longer to excrete the agent and hence result in a longer half-life.

An initial algorithm had been developed from the Pilot 2 study Group 1 data to convert measured fluorescence half-life data to GFR. Pilot 2 study Groups 2 and 3 refined this algorithm for efficacy and robustness, as well as adding to the algorithm database.

The sensor contains the light source for excitation of the tracer agent, the agent having a peak absorption wavelength of 440 nm. The detector is able to acquire the emission of the tracer agent, the agent having a peak emission wavelength of 560 nm. The sensor for the TGFR device is small and limited to the materials necessary for excitation and acquisition, and collection and processing of the data is conducted within the monitor. The device monitor displays the TGFR data.

3.2 Nonclinical Data

Available nonclinical study data on MB-102 support that the chemistry of the drug substance/drug product, and the manufacturing of the drug substance/drug product does not present a risk to human subjects. Additional information on the 24 nonclinical studies performed on MB-102 is found in the Investigator's Brochure.

3.3 Clinical Data

A total of 266 subjects have been treated with an IV administration of MB-102 across the three pilot studies (Pilot 1A, Pilot 1B and Pilot 2 Groups 1, 2 and 3). The Pilot 1 studies enrolled subjects with an eGFR indicating normal renal function. The Pilot 2 study enrolled subjects with normal renal function and those with renal function in the CKD stage 1-5 range. In addition, a total of 22 subjects (11 healthy volunteers and 11 Crohn's patients) have received a 4 or 8 µmol/kg oral dose of MB-102 in a study evaluating the use of MB-102 in the evaluation of gut permeability (MediBeacon Protocol 300-01). The total population exposure to MB-102 as of this protocol is 288 subjects. A total of 52 subjects (18.1% of the total population across 4 studies) were reported to have adverse events (AE). All reported events were mild or moderate in severity. No severe events have been reported, nor have any serious adverse events been reported or unanticipated adverse device effects.

There have been no clinically significant findings with regard to vital signs, physical exams or ECGs. Overall MB-102 administered intravenously at a dose of 4 μ mol/kg whether or not followed by a 5 mL (milliliter) dose of iohexol (OmnipaqueTM 300), or at a fixed dose of 130 mg

/ 7 mL (n=44) or consumed orally at a dose of 4 μ mol/kg (n=8) or 8 μ mol/kg (n=14) was well tolerated in the populations studied to date.

Adverse events related to the device itself were due to the adhesive materials used to hold the ORFM (Optical Renal Function Monitor) sensor in place. All device related events were considered mild or moderate in severity. For more information, please see the Investigator's Brochure.

MB-102 equilibrates between the vasculature and tissues post IV administration. The plasma pharmacokinetics show a peak concentration at the first sample time point. In Pilot 1A and Pilot 2, the first sample time point taken was approximately 5 minutes post administration; in Pilot 1B the first sample time point taken was approximately 30 minutes post administration. The fluorescence pharmacokinetics, reflecting the agent concentration in the tissue, has a peak fluorescence intensity in the range of 30 - 90 minutes, depending on the subject. MB-102 concentration equilibration between the vasculature and the tissue occurs approximately 30 - 60 minutes after the peak.

In the Pilot 2 Groups 1 and 2, the first blood draw was taken at 5 minutes post administration of MB-102, and the last at 12 hours post administration. The transdermal fluorescence was measured at the sternum and one other location for each subject using the prototype device QuantumLeap and Radiance. For all 120 subjects over the wide range of GFR values, the following were observed:

- A two-compartment plasma pharmacokinetic profile
- A high correlation between the MB-102 and iohexol plasma derived GFR values
- A high correlation between the MB-102 plasma and transdermal fluorescence pharmacokinetics

More information is available in the Investigator's Brochure and in Appendix I.

3.4 Study Rationale

This clinical study will evaluate the use of MB-102 and the MediBeacon[®] Transdermal GFR Measurement System for the purpose of marketing application with the final device design.

4 Study Objectives

The objectives of this pivotal study are:

- To establish that the MB-102 transdermal fluorescence measured GFR using the MediBeacon[®] Transdermal GFR Measurement System is comparable to the measured MB-102 plasma GFR
- To evaluate the safety and tolerability of a single dose of MB-102 in subjects
- To evaluate the safety and effectiveness of the MediBeacon[®] Transdermal GFR Measurement System for the non-invasive transdermal fluorescence detection of MB-102 in subjects

5 Investigational Plan

5.1 Overall Study Design and Plan

Protocol 100-003 is a multi-center, open-label, pivotal trial studying the safety and pharmacokinetics of MB-102 and the use of the MediBeacon[®] Transdermal GFR Measurement System in normal and compromised renal function subjects with different skin color types comparing tGFR to plasma derived indexed GFR (nGFR).

Approximately 250 subjects are planned for enrollment. The US sites will plan to enroll 140 evaluable subjects; China sites will enroll 48 evaluable subjects. The population will be split into stratums in accordance with eGFR by the CKD-EPI equation.

Subjects will be screened and if deemed eligible, will be enrolled. On treatment day, subjects will have a transdermal sensor placed on their chest, and the MediBeacon[®] Transdermal GFR Measurement System will be initiated to collect background fluorescence. When this is completed, subjects will then receive a single dose of MB-102. Serial PK draws will be collected over a 12 to 24 hour period. Fluorescent measurements will also be collected during this period. For subjects with significant renal compromise, fluorescent measurements will continue until the sensor no longer detects MB-102 in the body. Following completion of the treatment period, subjects will return to the study center approximately 1 week later for a safety follow-up visit.

Subjects who do not complete the study or who have major protocol deviations may be replaced. Up to 250 subjects may be enrolled.

The global study will include 188 evaluable subjects. The US enrolment will have 140 evaluable subjects. Once the US sites have enrolled the targeted number of evaluable subjects, the US clinical sites will be closed. The US data alone may be used to support the market authorization and approval in the US. The completed OUS dataset, if available will be included in the US application.

5.2 Overview of Study Procedures

Potential subjects will be screened for eligibility within 21 days prior to planned dosing. Based on their screening eGFR (measured using the CKD-EPI equation), they will be assigned to Stratum 1 or Stratum 2:

- Stratum 1: eGFR \geq 70 mL/min/1.73 m² (50% of subjects)
- Stratum 2: eGFR < 70 mL/min/1.73 m² (50% of subjects)

Following pre-dose procedures to ensure eligibility, one sensor will be affixed to the subject on the upper chest in the area between the shoulders (including the pectoralis and sternum area). The subject will then receive the MB-102 injection. MB-102 will be administered by IV injection over 30 - 60 seconds, followed by a saline flush IV over 30 - 60 seconds.

Stratum 1: PK sampling will be collected pre-dose and at 5, 15, 30, 60, 90, 120, 180, 240, 300,

360, 480, 600 and 720 minutes post-dose (12 hour collection period).

Stratum 2: PK sampling will be collected pre-dose and at 5, 15, 30, 60, 90, 120, 180, 240, 300, 360, 480, 600, 720 960, 1200, and 1440, minutes post-dose (24 hour collection period).

Safety assessments in the form of vital signs, safety labs, ECGs, and adverse event collection will occur during the dosing day.

Within 7 +/- 3 days of dosing, subjects will return to the study center for additional safety follow-up assessments.

5.3 Discussion of Study Design

The study is designed to validate the performance of the TGFR Measurement System.

5.4 Selection of Study Population

5.4.1 Number of Planned Evaluable Subjects

A total of 188 evaluable subjects are planned for enrollment. The population will be split into stratums accordance with eGFR by the CKD-EPI equation and location of enrollment:

- Stratum 1: 50% of subjects with an eGFR \geq 70 mL/min/1.73 m²
- Stratum 2: 50% of subjects with an eGFR < 70 mL/min/1.73 m^2

Subjects will be targeted across the spectrum of eGFR from normal through Stage 4 CKD. Subjects with an eGFR greater than 120 mL/min/1.73 m² or less than 15 mL/min/1.73 m² will be excluded. Efforts will be made to balance enrollment across the following eGFR levels such that each subcategory has minimum of 10 subjects:

- \geq 90 mL/min/1.73 m²
- $60 89 \text{ mL/min}/1.73 \text{ m}^2$
- $45 59 \text{ mL/min/1.73 m}^2$
- 30 44 mL/min/1.73 m²
- 15 29 mL/min/1.73 m²

Of the evaluable subjects, 140 will plan to be enrolled in the United States and 48 will plan to be enrolled at sites in China.

Approximately 50% of subjects within each stratum enrolled in the US will be Fitzpatrick skin scale (FSS) I-III and 50% of subjects will have FSS IV-VI. In the US, subjects will be targeted across the full spectrum of FSS (I - VI) such that FSS cohorts I-II, III-IV and V-VI will each enroll no less than 20 subjects.

The FSS will not apply to subjects enrolled in China because the population demographic is

unlikely to support the full FSS spectrum.

If subjects are not considered evaluable, they will be replaced in the study with a total potential enrollment up to 250 subjects.

5.4.2 Inclusion Criteria

To be eligible for study entry, all subjects must satisfy all of the following criteria:

Main Criteria for Inclusion:

- 1. Age \geq 18 years male or female
 - a. Eligible female non-pregnant subjects who are either not of child-bearing potential or willing to use adequate contraception during the trial
 - b. Males must be willing to practice abstinence or utilize adequate contraception from dosing day to at least 7 days post-dose
 - c. For women of child-bearing potential, the subject should have a negative serum pregnancy test at screening, and agrees to one of the following acceptable contraceptive methods used consistently and correctly i.e. abstinence, oral contraceptive either combined or progesterone alone; injectable progesterone, implants of levonorgestrel, estrogenic vaginal ring, percutaneous contraceptive patches, IUD device or system or male partner sterilization
 - d. Men will not donate sperm during the study and for 1 month following the last dose of study drug
- 2. Subjects who are capable of directly providing informed consent and who can comply with the requirements and restrictions required by the protocol
- 3. Adequate venous access sufficient to allow blood sampling per protocol requirements

5.4.3 Exclusion Criteria

To be eligible for the study, subjects must not meet any of the criteria noted below:

- 1. Subjects positive via PCR testing for COVID-19
 - a. Note: Vaccinated subjects without symptoms of COVID-19 are not required to undergo PCR testing but may be tested at the discretion of the study site
- 2. Recent donation or loss of blood or plasma: 100 mL to 499 mL within 30 days prior to the initial dose of the study medication; or more than 499 mL within 56 days prior to the initial dose of study medication
- 3. Non-steroidal anti-inflammatory (NSAID) use within 3 days of MB-102 dosing
- 4. The subject has participated in a clinical trial and has received an investigational product within the following time ranges: prior to the first dosing day in the current study: either 30 days or 5 half-lives of the investigational product (whichever duration is longer).
- 5. History of skin sensitivity to adhesives (e.g. Band-Aids, surgical tape)
- 6. History of severe allergic hypersensitivity reactions (unacceptable adverse events) or anaphylactoid reaction to any allergen including drugs, MB-102 or other related products (*intolerance to a drug is not considered a drug allergy*).

- 7. Any characteristics which, in the opinion of the investigator, makes the subject a poor candidate for participation in the clinical trial
- 8. Significant scaring, tattoos or alterations in pigmentation on the sternum or other sensor location testing areas that would alter sensor readings versus other areas of the skin
- 9. Any serious or uncontrolled medical disorder, active infection, physical exam finding, laboratory finding, or psychiatric condition that in the opinion of the investigator would limit the subjects' ability to complete study requirements or may put the subject at increased risk or compromise the interpretability of study results.
- 10. Currently receiving dialysis
- 11. Currently anuric
- 12. Positive serum pregnancy test
- 13. Subjects with an $eGFR > 120 \text{ mL/min}/1.73\text{m}^2$

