8.1 Investigational Drug

Clinical data from the Pilot 1A and 1B studies (total n = 32 subjects) included the following adverse events:

- Pilot 1A (n = 16)
 - Vasovagal reaction (1 subject)
 - Dizziness (1 subject, 2 events)

These events occurred in fasting subjects shortly after dosing and resolved on that day. No other AEs, injection site reactions, clinically significant laboratory values or significant changes in vital signs were noted during this study.

- Pilot 1B (n = 16)
 - Headaches (56.3% of subjects)
 - Erythema (at the site of the adhesive) (100% of subjects)
 - Diarrhoea (1 subject)
 - Dizziness (occurring in 1 subject following release from the study center)

Erythema was thought to be related to the adhesive used to adhere the sensor to the skin. Headaches were deemed related to the head strap required to hold the forehead sensor in place. Sensor placement on forehead was discontinued post Pilot 1B.

MB-102 is excreted in the urine. Therefore, urine discoloration (chromaturia) is expected but has not been considered an adverse event in prior studies.

In the Pilot 2 study, a total of 234 subjects with normal to compromised renal function have been exposed to MB-102. A total of 120 subjects received a dose of 4 μ mol/kg followed by a 5 mL injection of iohexol. Seventy (70) subjects received a single dose only (no iohexol) of 4 μ mol/kg of MB-102) and 44 have received a fixed dose of 130 mg (7 mL). All reported AEs were mild or moderate in severity and resolved without sequalae. Overall, MB-102 given in conjunction with or without iohexol was well tolerated in this subject population.

A total of 40 adverse events were reported in 28 treated subjects in Groups 1, 2 and 3 for an AE rate of 12.0% in the treated population. A total of 31 events were considered mild and 9 moderate events occurred in 5 subjects (2.5% of the population). There were no severe events

reported. There were no Serious Adverse Events (SAEs) reported during the study. There were no Unanticipated Adverse Device Effects (UADEs) reported during the study.

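### The eligibility rules and analysis sets do not keep Pilot 2 algorithm-development subjects out of the pivotal P30 set, so its independence is not assured

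*Combined protocol and SAP*

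**What the plan says.** Section 3.1 describes how the device's conversion was made: "An initial algorithm had been developed from the Pilot 2 study Group 1 data to convert measured fluorescence half-life data to GFR". It continues: "Pilot 2 study Groups 2 and 3 refined this algorithm for efficacy and robustness, as well as adding to the algorithm database". All three Pilot 2 groups are therefore development data. Section 8.1 gives the size of that study: "In the Pilot 2 study, a total of 234 subjects with normal to compromised renal function have been exposed to MB-102".

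Section 5.3 states the aim of the pivotal study: "The study is designed to validate the performance of the TGFR Measurement System". Success under 9.5 rests on one number, P30 of tGFR against plasma-derived indexed GFR. The lower 95% limit must exceed 85%, in a single arm.

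On earlier trial participation, 5.4.3 has only exclusion 4, which sets the interval since the last investigational product at "either 30 days or 5 half-lives of the investigational product (whichever duration is longer". No criterion addresses Pilot 2 participation or membership of the algorithm database. Section 6.11 limits repeat entry, but only within 100-003.

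In 9.2, the ITM set requires an end-of-session tGFR and no major deviation, and the mITM set (primary for effectiveness) also requires no outlier PK parameters. Neither refers to earlier participation in algorithm development, and no analysis without such subjects is planned.

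**The concern.** A washout deals with residual drug. It does nothing to separate the people on whom an algorithm was tuned from the people on whom it is tested. A returning subject brings back stable personal features, such as skin optics, body size and distribution volume, that were present in the development data. If the algorithm happens to suit those features, agreement in returners could be better than in new patients.

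The comparison with 85% has no control arm in which such optimism could cancel. Any advantage in returners would go straight into the P30 estimate and its lower limit. As the plan stands, a reader of the result could not tell whether this had happened, because overlap is not excluded, flagged or reported.

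**Working it through.** **1. Which limb of the washout governs.** Section 3.1 gives the half-life: "Normal functioning kidneys will remove this agent from the body with an approximate 2 hour half-life". Five half-lives are then 5 × 2 h = 10 h. The half-life limb would exceed 30 days only if the half-life were above 30 × 24 / 5 = 144 h. Section 3.1 says impaired kidneys take longer but gives no figure. For MB-102 the 30-day limb is in practice the rule.

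**2. The plan's sample size (9.7).** Inputs are true P30 0.95, goal 0.85, one-sided alpha 0.025, power 90% and an exact binomial test. For each n, the pass mark r is the smallest count with P(X ≥ r | n, 0.85) ≤ 0.025, and power is P(X ≥ r | n, 0.95). At n = 102, r = 94, exact alpha is 0.0231 and power is 0.930. Power first reaches 90% at n = 93 (0.906), drops below it at n = 95 to 101, and stays above it from 102 up to the largest n checked (199). The stated 102 is reproduced.

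**3. Pass marks at the planned sizes (9.9).** Section 9.5 names no interval method, so I assume the exact one that matches 9.7.
- N = 140 (US): r = 128, P(X ≥ 128 | 0.85) = 0.0170, exact lower limit at 128/140 = 0.855.
- N = 188 (global): r = 170, P(X ≥ 170 | 0.85) = 0.0194, exact lower limit at 170/188 = 0.853.

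**4. Effect of overlap.** The documents give neither the number of returners k nor their P30, so both are assumptions. With true P30 at 0.85 in new subjects and p in returners,

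P(success) = P(A + B ≥ r), where A ~ Bin(N − k, 0.85) and B ~ Bin(k, p).

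| N | k | p = 0.90 | p = 0.95 | p = 0.99 |
|---|---|---|---|---|
| 140 | 0 | 1.7% | 1.7% | 1.7% |
| 140 | 10 | 2.2% | 2.9% | 3.5% |
| 140 | 20 | 2.9% | 4.7% | 6.8% |
| 188 | 0 | 1.9% | 1.9% | 1.9% |
| 188 | 10 | 2.4% | 3.0% | 3.6% |
| 188 | 20 | 3.1% | 4.7% | 6.4% |

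For example, 20 of 140 at 0.95 moves the expected P30 from 0.850 to (120 × 0.85 + 20 × 0.95) / 140 = 121/140 = 0.864. At N = 140 the nominal 2.5% is first passed with 15 returners if p = 0.90 (2.48% at 14, 2.54% at 15) and with 8 if p = 0.95 (2.6%). Five returners at 0.99 leave it at 2.46%.

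**5. Power if overlapping subjects are left out.** Removing 20% of 140 without replacement leaves n = 112, with r = 103 and exact alpha 0.0206. Power at true P30 0.95 is 0.946, against 0.976 at n = 140. At true P30 0.93 it falls from 0.818 to 0.742.

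**The case against.** Much of the opposing case stands.

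- **Pool size.** A reader might infer that all 234 Pilot 2 subjects are eligible and outnumber the 188 planned. The documents do not support this. Section 3.3 puts Pilot 2 in CKD stages 1 to 5, while 5.4.1 excludes eGFR below 15 or above 120. Section 5.4.3 excludes dialysis and a history of adhesive sensitivity, and 8.1 reports seven Pilot 2 subjects with adhesive-related events. The eligible number is unknown and smaller than 234.
- **Are returners expected?** Exclusion 6 mentions "anaphylactoid reaction to any allergen including drugs, MB-102 or other related products", and a reader might take this as a sign that they are. It is a general allergy clause, and re-dosing within 100-003 under 6.11 is reason enough to name MB-102. Nothing in the documents describes re-contacting pilot volunteers.
- **Timing.** Section 5.6.1.2 dates the batch for Groups 1 and 2 to May 2015, and the Group 3 batch had already reached its 36-month stability point. The planned start here was Q2 2022. For much of Pilot 2 the gap is probably years, though dosing dates are not given.
- **Mechanism.** No data are re-used. A returner gives a new recording and a new plasma reference. The pivotal study uses the final device design (3.4), whereas Groups 1 and 2 were measured "using the prototype device QuantumLeap and Radiance". Nothing shows that the algorithm is fitted to individual features. Any leak would come only through stable subject characteristics.
- **Missing text.** Only the title of Appendix I is in the copy reviewed, so wording there on algorithm lock or independence cannot be ruled out.

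These points limit the likely size of the effect. They do not supply a rule that keeps development subjects out. Exclusion 7 (investigator opinion) permits that but does not require it.

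**Conclusion.** The point holds as a gap in design. In the text available, nothing secures the independence of the primary P30 set from the data that built the algorithm. It does not hold as a finding of bias: a reader might infer that P30 is inflated, but no document shows that any Pilot 2 subject was enrolled or that returners would agree better.

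The size depends entirely on two undocumented quantities, the number of returners and their P30 advantage. With a small overlap or a modest advantage, the chance of false success stays within the nominal 2.5%, for instance 2.2% with 10 of 140 at 0.90. With 20 of 140 it lies between 2.9% and 6.8% for P30 of 0.90 to 0.99. The top of that range assumes an advantage of 14 points, more than the 10-point distance between the performance goal and the design value. The change is worth making because it is cheap and answers a question that the result would otherwise leave open.

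**What to change.** Add to 5.4.3 an exclusion for any subject whose data were used to develop or refine the tGFR algorithm (Pilot 2 Groups 1 to 3), checked by one screening question.

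If any such subject is already enrolled, flag them on the eCRF, keep them in the safety analysis, and report P30 with and without them. State how they are handled in the primary set before P30 is analysed. The order matters because the study is open-label and 10.6 has sites record each tGFR, so a later choice could look driven by the data.

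The cost is one protocol line and one question. Former pilot volunteers would no longer be available for the eGFR and skin-type quotas. If overlapping subjects had to be left out of the US primary set, losing 20% without replacement would still leave about 94.6% power at true P30 0.95 (n = 112). The margin is thinner if the true value is lower: 74% at 0.93, against 82% at the full 140. The enrolment ceiling of 250 leaves room for replacement, although 5.4.1 and 5.4.5 would need to name this as a reason for it.
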